#### 14.2. Adverse Events and Serious Adverse Events

In this study, AEs and SAEs will be reported in all subjects from the time the subject signs the ICF until the completion of the safety follow-up/end of study visit. Treatment-emergent AEs and SAEs will be evaluated from study drug dosing until the end of study visit.

#### 14.2.1. Definition of Adverse Event

An AE is any event, side effect, or other untoward medical occurrence that occurs in conjunction with the use of a medicinal product in humans, whether or not considered to have a causal relationship to this treatment. An AE can, therefore, be any unfavorable and unintended sign (that could include a clinically significant abnormal laboratory finding), symptom, or disease temporally associated with the use of a medicinal product, whether or not considered related to the medicinal product. An AE may include an increase in severity of a pre-existing condition included in a subject's medical history, and symptoms or clinical sequelae of a suspected overdose. "Lack of efficacy" per se will not be reported as an AE or SAE. However, the signs and symptoms and/or clinical sequelae resulting from lack of efficacy will be reported if they fulfil the definition of an AE or SAE.

The Investigator should attempt to establish a diagnosis of the event based on the signs, symptoms, and/or other clinical information. In such cases, the diagnosis should be documented as the AE (and SAE if serious) and not the individual signs/symptoms.

## 14.2.1.1. Severity of an Adverse Event

Severity of adverse events will be assessed and reported following CTCAE Version 5.0 criteria (National Cancer Institute 2010). Severity of adverse events that do not match CTCAE criteria will be assessed as follows:

• Mild (Grade 1): awareness of sign or symptom but easily tolerated

- Moderate (Grade 2): discomfort enough to cause interference with usual activity
- Severe (Grade 3): incapacitating with inability to work or do usual activity
- Life-threatening (Grade 4): could reasonably lead to death without medical intervention
- Fatal (Grade 5)

## 14.2.1.2. Relationship of an Adverse Event to Study Drug

The Investigator will assess the relationship between study drug and the occurrence of each AE. The investigator's assessment of the relationship of each AE to study drug will be recorded in the source documents and the CRF. Alternative causes, such as medical history, concomitant therapy, other risk factors, and the temporal relationship of the event to the study drug should be considered and investigated, if appropriate. The following definitions are general guidelines to help assign grade of attribution:

- **Not related:** The event is clearly related to other factors such as the subject's clinical state, therapeutic interventions or concomitant drugs administered to the subject. This is especially so when an event occurs prior to the commencement of treatment with the study drug.
- Unlikely: The event was most likely produced by other factors such as the subject's clinical state, therapeutic interventions, or a concomitant drug administered to the subject and does not follow a known response to the study drug.
- **Possibly:** The event follows a reasonable temporal sequence from the time of study drug administration or follows a known response to the study drug but could have been produced by other factors such as the subject's clinical state, other therapeutic interventions, or concomitant drugs administered to the subject.
- **Related**: The temporal relationship is compelling between the administration of the study drug and the AE cannot be explained by the subject's medical condition or other therapies.

#### 14.2.1.3. Action Taken with Study Medications

Action taken with study medications will be recorded on the AE CRF page, as follows, regardless if a particular category is possible or not in this study:

- Dose Increased
- Dose Not Changed
- Dose Reduced
- Dose Interrupted
- Dose Withdrawn
- Not Applicable
- Unknown

#### 14.2.1.4. Outcome of an Adverse Event

Outcome of an AE will be recorded on the AE CRF as follows:

- Recovered/Resolved
- Recovering/Resolving
- Recovered/Resolved with Sequelae
- Not Recovered/Not Resolving
- Fatal
- Unknown

#### **14.2.2.** Definition of Serious Adverse Event

A serious adverse event (SAE) is any untoward medical occurrence that at any dose:

- Results in death
- Is life-threatening
- Requires inpatient hospitalization or prolongation of existing hospitalization
- Results in persistent or significant disability/incapacity, or
- Is a congenital anomaly/birth defect.

Important medical events that are not one of the above may be considered to be SAEs by the investigator when, based upon appropriate medical judgement, they are considered to be clinically significant and may jeopardize the subject, or when medical or surgical intervention may be required to prevent one of the outcomes listed above.

An AE is considered "life-threatening" if, in the opinion of either the Investigator or the Sponsor, its occurrence places the subject at immediate risk of death. It does not include an AE that, had it occurred in a more severe form, might have caused death.

It is important to distinguish between serious and severe AEs. Severity is a measure of intensity, whereas seriousness is defined by the criteria under Section 14.2.2. An AE of severe intensity may not be considered serious.

## 14.2.3. Pregnancy

The Investigator must report to the Sponsor any pregnancy occurring in a study subject (or subject's partner) during the subject's participation. The report should be submitted within the same timelines as an SAE, although a pregnancy per se is not considered an SAE unless the birth results in a congenital anomaly/birth defect or there is suspicion that the study medication may have interfered with the effectiveness of a contraceptive medication or method. Spontaneous miscarriages should also be reported and handled as SAEs. Elective abortions without complications should not be handled as AEs.

A pregnancy should be followed-up until reporting of the pregnancy's outcome and the birth date.

As information is available, a pregnancy diagnosed during the study will be reported immediately to the Investigator and Sponsor (or designee), including pregnancy in female partners of male subjects. The pregnancy will be followed to term or outcome and this outcome will be reported to the Sponsor.

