PTG-300 was also evaluated for embryo-fetal development toxicity in rats and rabbits and fertility and early embryonic development toxicity in both male and female rats. The maternal NOAEL was 3 mg/kg/dose and the NOAEL for the embryo-fetal development was 0.3 mg/kg/dose in the definitive embryo-fetal development toxicity study in rats. The maternal NOAEL was 1 mg/kg/dose and the NOAEL for the embryo-fetal development was 0.3 mg/kg/dose in the definitive embryo-fetal development toxicity study in rabbits. The NOAEL for paternal toxicity and the NOEL for effects on male fertility and early embryonic development were considered to be 10 mg/kg/dose in fertility and early embryonic development toxicity study in male rats. The NOAEL for maternal toxicity and the NOEL for effects on female fertility and early embryonic development toxicity study in female rats.

Principle findings in nonclinical toxicology studies are alterations in red cell mass. PTG-300 has no apparent effect on cardiovascular, respiratory, or neurobehavior in safety pharmacology studies. PTG-300 is not genotoxic.

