## 7. INVESTIGATIONAL PLAN

# 7.1. Overall Study Design

This is a multicenter, single-arm, open-label study in subjects with HH. Subjects will receive subcutaneous PTG-300 for up to 24 weeks. Subjects will start at an initial dose of 10 mg per week subcutaneously. The dose may be increased to 20 mg per week, and subsequently to 40 mg and to 80 mg per week if needed, based on tolerability and the pharmacodynamic marker TSAT. In addition, subcutaneous dosing schedules of 10 mg, 20 mg, and 40 mg twice weekly (Day 1 and either Day 4 or Day 5) may be tested.

Based on a review of the TSAT and safety data from at least the first 4 subjects, the starting dose and/or the dosing regimen may be modified for subsequent subjects to reduce exposure to ineffective doses.

Subjects' safety and blood iron parameters (serum iron, serum ferritin, transferrin, and TSAT) will be collected to monitor the pharmacodynamic effect of PTG-300. Effect on phlebotomy need and quality of life (QoL) data (36-Item Short Form Health Survey [SF-36], and Patient's Global Impression of Change [PGI-C]) will also be collected and tabulated.

A subset of subjects (approximately 6 subjects) will participate in a sequential two-way crossover iron (Fe) absorption substudy. The oral iron absorption substudy will be conducted once during the 3-week screening period and then following approximately 4 to 6 weeks of PTG-300 treatment.

Subjects will participate in this study for up to 31 weeks as follows:

- Screening: Up to 3 weeks
- PTG-300 Treatment: Up to 24 weeks (may include iron absorption substudy for selected subjects)
- Safety follow up: 4 weeks.

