# 7.1.4. Post-Treatment / Early Termination Safety Follow-Up (Week 29)

Subjects who complete the treatment or who discontinue treatment early will undergo Visit 8/end of treatment (EOT) assessments as well as follow-up safety evaluations approximately 4 weeks after the last dose of study drug (Visit 9/end of study [EOS]).

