## 8. SELECTION AND WITHDRAWAL OF SUBJECTS

# 8.1. Subject Inclusion Criteria

Subjects must meet ALL of the following inclusion criteria to be enrolled:

- 1. Male and female subjects aged 18 years or older.
- 2. Have a confirmed diagnosis of HFE-related hereditary hemochromatosis with prior genotype testing.
- 3. Documented stable phlebotomy for ≥6 months prior to screening; with a phlebotomy frequency of at least 0.25 per month (e.g., received at least three phlebotomies over the previous 12 months, or at least four phlebotomies over the previous 15 months) and a phlebotomy frequency of less than 1 per month.
- 4. Screening hemoglobin >11.5 g/dL.
- 5. Serum ferritin <300 ng/mL at screening (before screening phlebotomy).
- 6. Women of childbearing potential (WOCBP) and men with partners of childbearing potential agree to use a highly effective contraceptive measure (based on the Clinical Trials Facilitation Group [CTFG]) during the duration of the study and for 28 days after the last dose of study drug in the case of women and 90 days after the last dose of study drug in the case of men.
- 7. Subject understands the study procedures, is willing and able to adhere to study requirements and agrees to participate in the study by giving written informed consent.

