## 10.2.1. Contraceptive Requirements

Women of childbearing potential (WOCBP) and men must use medically acceptable contraception (<1% annual failure rate) during the duration of the study and for 28 days after the last dose of study drug in the case of women and 90 days after the last dose of study drug in the case of men. Medically acceptable methods of contraception that may be used by the subject and/or partner include but are not limited to the following:

- Combined (estrogen and progesterone containing) hormonal contraceptives (for at least 3 months before screening) (oral, intravaginal, or transdermal)
- Progesterone-only hormonal contraception (oral, injectable, or implantable) associated with inhibition of ovulation
- Intrauterine device (IUD)
- Intrauterine hormone-releasing system (IUS)
- Surgically sterile (e.g., vasectomy, hysterectomy, bilateral salpingectomy, or bilateral oophorectomy at least 3 months before dosing)
- Sexual abstinence.

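### Partner-pregnancy reporting stops at Visit 9, about 62 days before the 90-day male contraception period ends, and Section 14.2.3 gives two different scopes for what is reportable

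*Combined protocol and SAP*

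**What the plan says.** **Reporting rule.** Section 14.2.3 requires the investigator to report "any pregnancy occurring in a study subject (or subject's partner) during the subject's participation". Later in the same section the scope is put differently: "a pregnancy diagnosed during the study will be reported immediately to the Investigator and Sponsor (or designee), including pregnancy in female partners of male subjects". A reported pregnancy is then followed to its outcome. Miscarriages are handled as serious adverse events (SAEs), and a pregnancy counts as an SAE if the birth results in a congenital anomaly.

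**End of participation.** Section 7.1 states: "Subjects will participate in this study for up to 31 weeks as follows". It lists up to 3 weeks of screening, up to 24 weeks of treatment and "Safety follow up: 4 weeks". Section 7.1.4 and footnote c of Table 2 put Visit 9 (end of study) about 4 weeks after the last dose, for completers and early terminators alike. Section 14.2 ends adverse event and SAE reporting at that visit.

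**Contraception.** Inclusion criterion 6 in Section 8.1 applies for the duration of the study, then for 28 days after the last dose in women and "90 days after the last dose of study drug in the case of men". Section 10.2.1 repeats both durations.

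**The concern.** For men, the protocol sets a post-dose precaution period of 90 days but collects pregnancies for only about the first 28 of them. A partner pregnancy conceived in the remaining days lies inside the period the protocol treats as relevant and outside its reporting rule.

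No other provision closes the gap. SAE collection stops at the same visit. Follow-up to outcome applies only to pregnancies already reported. The serum pregnancy test at Visit 9 is for women of childbearing potential, and Table 2 schedules no question about partners.

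The second difficulty is the pair of scopes in Section 14.2.3. A conception shortly before Visit 9 that is recognised afterwards appears to fall under the first sentence (it occurred during participation) but not under the later one (it was not diagnosed during the study). Two sites could apply the section differently.

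At stake is the completeness of a small body of safety data: the outcomes of any partner pregnancies conceived within the stated contraception period.

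**Working it through.** This is calendar arithmetic; no sample-size formula applies.

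**The plan's own figure.** Participation = 3 + 24 + 4 = 31 weeks, which reproduces the stated total. Post-dose participation = 4 weeks = 28 days.

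**Men, nominal timing.** 90 − 28 = 62 days without a reporting requirement; 62/90 = 68.9% of the post-dose period.

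**Men, other visit timings.** The ±2-day window is footnote b of Table 2. Day 197 is assumed as 28 days after the Day 169 end-of-treatment visit (169 + 28). The last-dose days are assumed from a 24-week course starting on Day 1.

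| Visit 9 timing | Days after last dose | Gap (days) | Share of 90 |
|---|---|---|---|
| 2 days early | 26 | 64 | 71.1% |
| Nominal | 28 | 62 | 68.9% |
| 2 days late | 30 | 60 | 66.7% |
| Day 197, last dose Day 166 (twice weekly) | 31 | 59 | 65.6% |
| Day 197, last dose Day 165 (twice weekly) | 32 | 58 | 64.4% |
| Day 197, last dose Day 162 (weekly) | 35 | 55 | 61.1% |

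**Men, against the whole contraception period.** Contraception is required during the study as well. Counted from first dose to 90 days after the last dose, the period is (162 − 1) + 90 = 251 days up to (169 − 1) + 90 = 258 days. Then 62/251 = 24.7% and 62/258 = 24.0%. Adding up to 21 days of screening lowers the share slightly: 62/(258 + 21) = 22.2%.

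**Women.** 28 − 28 = 0 days. The two windows coincide nominally, so only the question of late recognition remains.

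**Expected number of events.** As an extreme assumption, take all 28 planned subjects (Section 7.3) as men with partners of childbearing potential. Section 10.2.1 asks for methods with an annual failure rate below 1%. At 1%, 28 × 0.01 × 62/365 = 0.05 partner conceptions in the gap. At an assumed 5%, 28 × 0.05 × 62/365 = 0.24.

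**The case against.** The case on the other side is mostly about size and meaning, and much of it stands.

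- **Share of the window.** A reader might infer that most of the male risk window goes unreported. That holds only for the 90-day post-dose tail. Against the full contraception period, which includes treatment, the gap is about a quarter. The rule also does not forbid a report; it simply does not require one.
- **Toxicology.** A reader might take the gap to be more serious because "the NOAEL for the embryo-fetal development was 0.3 mg/kg/dose in the definitive embryo-fetal development toxicity study in rats", with the same value in rabbits, against higher maternal levels. Those studies speak to exposed pregnant females. For male exposure, Section 5.2.1 gives 10 mg/kg/dose both for paternal toxicity and for male fertility and early embryonic development, and it describes the drug as not genotoxic. The maternal and embryo-fetal figures therefore do not measure the consequence of a partner gap.
- **Female subjects.** A reader might infer a comparable gap for women. The documents do not support one: the windows coincide, and the first sentence of Section 14.2.3 arguably already covers a conception before Visit 9 that is found later. What remains is the ambiguity between the two sentences.
- **Empty reporting.** A reader might conclude that the study would report no pregnancies. It would not follow: those in subjects and partners through Visit 9 stay reportable and are followed to outcome.
- **Consequence.** Expected events are few, and no efficacy estimate, analysis set or planned safety table changes. This argues for a low severity.

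None of these points supplies a provision that extends partner reporting beyond Visit 9.

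**Conclusion.** The mismatch is in the text. About 62 post-dose days (55 to 64 across the timings examined) lie inside the male contraception period but outside the partner-pregnancy reporting requirement. Separately, Section 14.2.3 leaves it unclear whether a conception before Visit 9 that is recognised later is reportable.

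The conclusion assumes that participation ends at Visit 9, as the 31-week breakdown in Section 7.1 implies, and that the contraception durations in Sections 8.1 and 10.2.1 mark the period the sponsor regards as relevant. It takes no view on whether those durations are right. The argument is one of internal consistency, not evidence of male-mediated harm.

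Severity is minor. It is worth correcting because the correction is cheap and any such pregnancy outcome would otherwise be captured only by chance.

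**What to change.** 1. In Section 14.2.3, keep the present scope of the subject's participation and add: *and until the end of the applicable contraception period stated in Sections 8.1 and 10.2.1, including pregnancies conceived in that period and diagnosed later*. Keeping the present start matters, because a scope beginning at first dose would drop screening, which is now covered.
2. Reword the later sentence on pregnancies diagnosed during the study so that it carries the same scope.
3. In Section 14.2, state that outcomes of these pregnancies that are handled as SAEs remain reportable after the end-of-study visit. Otherwise a miscarriage after Visit 9 would meet two conflicting rules.
4. At Visit 9, remind male subjects to tell the site of a partner pregnancy conceived within the contraception period.

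**Cost.** A few sentences and a reminder, with no new visit or test. Sites keep a passive reporting duty for about two months (62 days, roughly 9 weeks) after a male subject's last visit. Capture would still depend on the subject volunteering the information.

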#### 14.2.4. Other Safety Parameters and Related Information

Additional safety parameters (laboratory tests including CBC, 12-lead ECGs, physical examinations, and vital signs) and concomitant medications are collected as shown in the Schedules of Assessments in Table 2. Clinical laboratory assessments are listed in Appendix 1.

Abnormal findings, other than pharmacodynamic markers, that are deemed clinically significant or are associated with signs and/or symptoms must be recorded as AEs (or recorded as an SAE if they meet the criteria of being serious) as described previously.

The Investigator should exercise his/her medical and scientific judgment in deciding whether an abnormal laboratory finding or other abnormal assessment is clinically significant. Usually, the abnormality should be associated with a clinically evident sign or symptom.

A clinically significant laboratory abnormality in the absence of clinical signs and symptoms may jeopardize the subject and may require intervention to prevent immediate consequences. For example, a markedly low serum glucose concentration may not be accompanied by coma or convulsions, yet be of a magnitude to require glucose administration to prevent such sequelae.

## 14.3. Recording Adverse Events

Adverse events spontaneously reported by the subject and/or in response to an open question from the study personnel or revealed by observation will be documented in the medical record in accordance with the Investigator's normal clinical practice and on the AE page of the case report form (CRF). SAEs that occur during the study must be documented in the subject's medical record, in the AE CRF, and on the SAE form.

If there is evidence of an AE or SAE through report or observation, the Investigator or designee will evaluate further and record the following information:

- Time of onset and resolution
- Severity
- Causality/relation to study treatment
- Action taken regarding study drug
- Outcome

## 14.4. Reporting Adverse Events

**Adverse Events**: All AEs, regardless of their relationship to PTG-300, will be reported on the AE Case Report Form. In order to ensure timely safety oversight of the trial, AEs should be reported routinely. All reports should include time of onset and resolution, severity (see Section 14.2.1.1), relationship to PTG-300, action taken regarding PTG-300 and outcome.

**SAEs**: In order to meet the requirements for expedited reporting of SAEs to applicable regulatory authorities and IRBs, all SAEs, must be reported to the Sponsor within 24 hours from the time the site investigational team first becomes aware of the event. This report may be initially achieved by telephone, or by completing a SAE report form and sending it to the Sponsor via the contact information printed on the form.

The SAE report form should be completed as thoroughly as possible and signed by the Investigator before transmittal to the study Sponsor. It is very important that the Investigator provide an assessment of the causal relationship between the event and study drug at the time of the initial report, as this will be useful for submissions to regulatory authorities.

Initial notification of an SAE by telephone must be confirmed in writing 24 hours from the time the site investigational team first become aware of the event using the SAE report form as described above.

As further information regarding the SAE becomes available, such follow-up information should be documented on a new serious adverse event report form and marked as a follow-up report.

Protagonist is responsible for notifying the relevant regulatory authorities of certain events. It is the Principal Investigator's responsibility to notify the IRB or IEC of all SAEs that occur at his or her site. Investigators will also be notified of all unexpected, serious, drug-related events (7/15 Day Safety Reports) that occur during the clinical trial. Each site is responsible for notifying its IRB or IEC of these additional SAEs.

